Study protocol

Health care characteristics and quality of care for atopic dermatitis in Germany

Principal investigator:

Univ.-[name]. [name] Director, Institute for Health Services Research in Dermatology and Nursing (IVDP) University Medical Center Hamburg-Eppendorf (UKE) [name], Germany

In cooperation with:

[name]. [name] University Hospital, Technical University Dresden

German Center for Health Services Research in Dermatology

Institute for Health Services Research in Dermatology and Nursing (IVDP) University Medical Center Hamburg-Eppendorf (UKE) [name] E-Mail: [contact] [contact], Fax: [name]

1 Synopsis

Study title	"AtopicHealth2" - Health care characteristics and quality of care		
	for atopic dermatitis in Germany		
Condition	Atopic dermatitis		
Objective	Generating routine data on quality of care, treatments needs, and guideline- compliant care for atopic dermatitis from the patient's and the physician's perspective		
Design	Non-interventional, multi-center, cross-sectional health care study in patients with atopic dermatitis under medical care		
Estimated number of participants	N = 1,500 adult patients with atopic dermatitis in medical care		
Inclusion criteria	 Diagnosed atopic dermatitis Patient understands the survey and is expected to be able to complete the questionnaire Patient gives written consent on participation Patient has signed the data protection declaration 		
Exclusion criteria	Lack of mental, physical or linguistic ability to participate in a questionnaire survey		
Main Outcomes	1. Severity levels		
	2. Health care situation and quality of care		
	3. Patient benefit of the ongoing therapy and compliance		
	4. Health economic outcomes		
Study duration	Appr. 100 weeks		
Observation period	One visit (cross-sectional study)		
Work packages	The following study periods are planned (some periods may be overlapping): Study preparation (incl. obtainment of ethics vote): 10 to 16 weeks Center recruitments: 8 weeks First patient inclusion: tbd Last patient inclusion: tbd Overall recruitment period: 52 weeks Final data management period: 4-12 weeks after last patient out Determination of assessed cost parameters: 4-8 weeks Data analysis: 4-8 weeks Final report: 4 weeks		
Statistical analysis	All data will be analysed with descriptive statistics and specified in terms of statistical standard values. Further statistical analyses will be performed		

4.2 Cooperation

[name]. [name] University Hospital, Technical University Dresden

5 Introduction

Atopic dermatitis is one of the most common chronic diseases in Germany. Within the last three decades, the prevalence has doubled or even tripled in industrial countries (Ring et al. 2010). Reported prevalence rates range between 5 to 20 % among children (Carroll et al. 2005) and 1.13 to 4% among adults (Schaefer et al. 2008; Schmitt; Radtke et al. 2016). In the mid of the years 2000, clinicians often experienced that despite the comparably wide therapeutic spectrum of available topical agents, systemic drugs and physical procedures, patients expressed dissatisfaction concerning the treatment of their illness. Patients lamented the lack of sustainable effectiveness of the therapies, the difficulty concerning treatment, myriad side effects as well as the insufficient response regarding the treatment of patients severely affected. Due to poorly developed health services research in Germany, there were only few scientific analyses concerning these findings. These findings induced the first national study on AD in Germany called "AtopicHealth1" (Langenbruch et al. 2014). Data from this first large-scale study conducted in 2010 in dermatological practices, indicates that 13.3 % of the patients ranked the health care of the last years as "poor" or even "deficient". At the same time, 82.1 % were "very content" or "content" with their previous treatments. Measured with the patient benefit index, 88.4 % of patients received a relevant benefit from their therapy. One third of the study population displayed a high impact of their atopic dermatitis on the perception of their global health state and the guality of life. The high disease-related daily burden was mostly caused by sleeplessness due to itching, what indicates insufficient treatment regimes in this case. A high percentage of patients used topical steroids and emollients. That indicates that many patients did not receive the necessary modern therapeutics for the treatment of their atopic dermatitis. At the same time, the necessary measures according to clinical guideline (Werfel et al. 2016) and scientific evidence are not implemented sufficiently. (Steinke et al. 2014; Langenbruch et al. 2014) First results from the German Atopic Eczema Registry TREATgermany showed that Ciclosporin is the most commonly used therapeutic agent among patients with severe atopic dermatitis - not least because it is the only agent explicitly approved for the treatment of severe atopic dermatitis (Schmitt et al. 2016).

All in all the data at hand partially speaks for a shortage of care for patients with atopic dermatitis. In this case the hesitant, partially due to unawareness and uncertainty, prescription of medical treatment by pediatricians and some dermatologists may contribute.

A further barrier concerning the implementation of innovative medication in atopic dermatitis care derives from unclear definition of "high need" in routine care. Furthermore there are practically no data in Germany concerning the matter of patient-compliance with therapeutics. This compliance however poses a crucial economic factor in therapy (Lewis und Finlay 2004). In this respect, for the benefit of an appropriate care for severely affected patients with atopic dermatitis, measures that enforce a rapid access to these drugs must be initiated. These measures require an assurance via sound data, especially knowledge of health care from the patient's perspective.

Important key aspects of the patient's perspective are a) the subjective burden of disease, b) the need for humane medical care, c) the experienced quality of care, d) the assessment of the benefit of the appropriated medical performances from the patient's perspective, e) the compliance and "empowerment" of the patient.

5.1 Preliminary Research

The national care evaluation study AtopicHealth1 has provided pioneering methodological and contentrelated prior knowledge, which will be fully appointed in the study at hand. Resulting from the research, the following scientific papers were published:

The scientific findings will be used for planning the Study "AtopicHealth2", the initial data will be used as a reference for the further assessment of care for 2017. Other preliminary studies on atopic dermatitis at the German Center for Health Services Research in Dermatology (CVderm) and the University Hospital of Dresden are also taken into account; subsequent an extract summary:

Study	Year	Target group	Study type	Data source	Number of cases (n)
AtopicReal * (Beikert et al. 2014)	2008-09	pat. in self- help groups	survey	self-help	384
AtopicHealth 1* (Langenbruch et al. 2014; Steinke et al. 2014)	2010	pat. in derm. care	survey + examination	practices & clinics	1,678
AtopicCare ad * (Radtke et al. 2016)	2009	insured ≥ 18 years	secondary data analysis	Barmer GEK	48,140/ 1.64 Mio.
AtopicCare juv * (Augustin et al. 2015)	2009	insured < 18 years	secondary data analysis	Barmer GEK	30,354/ 293,181
AtopicWork *	2001-2015	working population	survey + examination	companies in Germany (>400)	2,064/ 147,117
AtopicPub * (Augustin et al. 2013)	2012	general population	public poll	FORSA	46/1,004
Atopic Eczema Registry "TREATgermany" ** (Schmitt et al. 2016)	since 2011	severe AD	register	dermatological centers	78 (December 2015)

Table 1: Previous studies on health care for atopic dermat	itis in Germany at the CVderm in
Hamburg (*) and at the University of Dresden (**)	-

5.2 Goal and benefit of the study

The aim of the present planned study "AtopicHealth2" is the generation of up-to-date scientific data concerning the quality of care for atopic dermatitis in Germany. A particular focus lies upon the description of ongoing therapies, quality of life and individual treatment needs and benefits from the patient's perspective. Adult patients with all levels of severity and age groups are included. The Study is methodologically and contend-relatedly tied to the first national health care evaluation study AtopicHealth1. With these data, concerns about care from the patient-side as well as supply gaps can be characterized further and measures can be reached on different levels.

The planned study represents an outstanding occurrence in German health services research, as it is a continuation of the study AtopicHealth1, conducted in 2010, capturing the standard of care for atopic dermatitis from the patient's perspective with representative data, allowing comparisons over a period of more than 6 years. The results of the study intend to serve the scientific analysis of the current supply of care with topical therapy and systemic drugs and are applicable in the argumentation towards prescribers, users, cost bearers and decision-makers in health care policy ("health economic positioning"). Furthermore, the data serves acquiring knowledge regarding the preferences and application behavior of patients with atopic dermatitis. Multiple usage of the generated data is strived at.

Thus the study shows several significant benefits for the patients and supplying physicians:

- 1. The nationwide survey concerning the subjective burden of disease allows assessment of patient "distress" and the need for care concerning atopic dermatitis.
- 2. As an inventory control of the current care, the study enables an acquisition of the existing supply gap with solid data.
- 3. Due to profiling of the "poorly cared-for patient" and his or her needs, the study facilitates future care provision planning.
- 4. The recorded predictors of "poor care" are requirements for the targeted dismantling of "care barriers" to date, a not yet introduced strategy in Germany.
- 5. Due to the acquisition of quality indicators and benefit assessment from the patient's perspective, the study allows a profound analysis of the benefit as perceived by the patient of the hitherto appointed types of therapy.
- 6. Acquisition of statements from the patient-side regarding compliance enables the articulation of patient-side predictors of non-compliance aiming at an efficient patient supervision.
- 7. In analogy to the care evaluation study for psoriasis, the study at hand also identifies regional differences in care and further makes this a subject of discussion.
- 8. With the knowledge gained, a profound health-policy-related argumentation is enabled.

6 Study protocol

6.1 Study design

Open, multicenter cross-sectional observational study with at least n=1500 patients with atopic dermatitis of all types and all levels of severity.

6.2 Objectives

Concerning the current study, the following questions will be clarified:

- How high is the subjective burden of disease of patients with atopic dermatitis in 2016/2017 in Germany?
- 2. What are the patient-specific needs in the course of medical care?
- 3. How is the quality of care for different levels of severity and therapeutic groups of the disease?
- 4. What kind of quality does the care measured via guideline compliant quality indicators and single items demonstrate compared to 2010?
- 5. How is the benefit of the medical services assessed from the patient's perspective?
- 6. To what extent are restrictions of compliance perceived from the patient's perspective and how are these explained?
- 7. To what extent is there an undersupply, particularly regarding treatment with systemic drugs?
- 8. Which predictors can be found for a proficient/poor care for atopic dermatitis patients?
- 9. How high are the costs-of-illness caused by atopic dermatitis and which predictors can be found?
- 10. Which impact does atopic dermatitis have on workability?

6.3 Patients

6.3.1 Number of patients

The study will include 1,500 up to 2,000 adult patients, to be recruited by about 100 active sites. Approximately 50 sites are required to include patients with all levels of severity. The remaining sites should only include patients with severe atopic dermatitis.

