6.9 Statististical analysis

All data will be analysed with descriptive statistics and specified in terms of statistical standard values (absolute and percentage frequencies for categorical data; min, max, mean, standard deviation, median for continuous data). Further statistical analyses will be performed according to the study questions. In particular, the outcomes of different subgroups will be compared and predictors for specific outcomes will be determined by application of adequate significance tests. Data analyses will be conducted by means of IBM SPSS Statistics for Windows, Version 23 (IBM Corp., Armonk, NY, USA).

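### Severe-only recruitment at about half the sites shifts pooled, severity-dependent estimates that the protocol calls representative and comparable with 2010

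*Protocol*

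**What the plan says.** Section 6.3.1 sets the size and the split: "The study will include 1,500 up to 2,000 adult patients, to be recruited by about 100 active sites". It continues: "Approximately 50 sites are required to include patients with all levels of severity", and then "The remaining sites should only include patients with severe atopic dermatitis". It does not say how many patients each type of site should supply, or how severe disease is to be recognised at recruitment.

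The rest of the protocol does not carry the split forward:

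- Section 6.1 describes a single sample of "at least n=1500 patients with atopic dermatitis of all types and all levels of severity". The synopsis does not mention two site types.
- Section 6.3.2 lists age, diagnosis, ability to complete the survey, consent and the data protection declaration. It has no severity condition for any site.
- Section 5.2 says the study captures the standard of care "with representative data, allowing comparisons over a period of more than 6 years". Section 5.1 makes the 2010 study the reference, and its Table 1 lists that study as 1,678 patients in dermatological care, from practices and clinics.
- Section 6.2 asks national questions, for example "How high is the subjective burden of disease of patients with atopic dermatitis in 2016/2017 in Germany" (Objective 1), and Objective 4 asks for a comparison with 2010.
- Section 6.9 states: "All data will be analysed with descriptive statistics and specified in terms of statistical standard values". It adds further analyses by study question, including subgroup comparisons, but names neither site type nor weighting.

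**The concern.** Sending about half the sites after severe patients only is deliberate over-sampling. That is a legitimate way to learn more about severe disease, but the pooled sample then no longer has the severity mix of patients in care. Any overall mean or rate that varies with severity moves towards its value in severe patients, by an amount set by how many patients the severe-only sites deliver.

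The objectives exposed are 1 (burden), 4 (quality compared with 2010), 5 (benefit), 7 (undersupply, particularly of systemic drugs), 9 (costs) and 10 (workability), each as far as its outcome depends on severity. The 2010 benchmarks in the Introduction (13.3% rating care as poor or deficient, 82.1% content or very content, 88.4% with relevant benefit) are whole-sample figures. If the later sample is enriched and the earlier one was not, a difference can appear without any change in care. Section 6.7 expects very high power even for small effects, so a modest artefact could reach significance. Section 5.2 intends the results for argument towards cost bearers and policy makers.

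**Working it through.** **Inputs from the protocol.** 1,500 to 2,000 patients at about 100 sites (an average of 15 to 20 per site); about 50 sites for all severities, the rest severe only (6.3.1); 1,678 patients in 2010 (Table 1 and 6.6.1); 13.3% poor or deficient ratings in 2010 (Introduction).

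**Inputs that must be assumed.** w, the share of patients from severe-only sites: 0.5 (equal recruitment per site), 0.25 or 0.1. s, the severe share at all-severity sites: 10% to 40%. D, the severe minus non-severe difference in the outcome. Two-sided alpha 0.05; clustering by site ignored.

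**Step 1, the plan's own figure.** Section 6.7 states power up to 100% at n = 1,500 but gives no test, alpha or effect size, so it cannot be reproduced exactly. It is plausible. For 1,500 against 1,678 patients, power is 80% at a standardised difference of 0.1 and 99.99% at 0.2.

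**Step 2, severity mix.** Pooled severe share = w + (1 − w)s. The excess over s is w(1 − s), so the shift in a pooled mean or rate is w(1 − s)D.

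| w | pooled severe share, s = 10% / 20% / 30% / 40% | shift |
|---|---|---|
| 0.5 | 55% / 60% / 65% / 70% | 0.45D / 0.40D / 0.35D / 0.30D |
| 0.25 | 32.5% / 40% / 47.5% / 55% | 0.225D / 0.20D / 0.175D / 0.15D |
| 0.1 | 19% / 28% / 37% / 46% | 0.09D / 0.08D / 0.07D / 0.06D |

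**Step 3, consequence for a 2010 comparison.** Suppose nothing has changed since 2010, the 2010 sample was not enriched, s = 20% and D = 10 points. The non-severe rate is then 13.3 − 0.2 × 10 = 11.3% and the severe rate 21.3%. At w = 0.5 the pooled rate is 0.6 × 21.3 + 0.4 × 11.3 = 17.3%. The standard error of the difference is sqrt(0.133 × 0.867/1678 + 0.173 × 0.827/1500) = 1.28 points, so the expected z is 4.0/1.28 = 3.12. The chance of z above 1.96 is about 88%.

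| w | pooled rate | falsely significant rise, D = 10 | with D = 5 | with D = 15 |
|---|---|---|---|---|
| 0.5 | 17.3% | 88% | 36% | 99.6% |
| 0.25 | 15.3% | 36% | 13% | 66% |
| 0.1 | 14.1% | 10% | 5% | 16% |

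The nominal rate in this direction is 2.5%. With D = 10 and s running from 10% to 40%, the figures are 94% to 66% at w = 0.5, 44% to 23% at w = 0.25, and 11% to 7% at w = 0.1.

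**Step 4, precision after the change.** The all-severity sites alone give n of about 750 at w = 0.5. The 95% half-width for a 50% proportion is 1.96 × sqrt(0.25/750) = 3.6 points, against 1.96 × sqrt(0.25/1500) = 2.5 points. If all patients are weighted instead, effective n = 1/(s²/n_sev + (1 − s)²/n_non). With s = 20% and w = 0.5 there are 900 severe and 600 non-severe patients, giving 1/(0.04/900 + 0.64/600) = 900. Over s = 10% to 40% the range is 825 to 1,050. Power against 2010 with 750 patients is still 99.5% at a standardised difference of 0.2.

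**The case against.** The strongest reply has four parts.

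- **Weights and stratification belong in an analysis plan.** None is shown here, and one may exist. Section 6.9 leaves room for analyses by study question and by subgroup, SCORAD is a planned outcome, and the planned regional comparison implies that sites are traceable. So most of the bias could be handled at analysis. This stands as to method. It does not remove the conflict within the protocol between the enrichment in 6.3.1 and the claims in 5.2 and 6.1, and a later plan cannot supply a common recruitment definition of severe disease after patients are enrolled.
- **Not all results are affected.** A reader might infer that every population-level figure is shifted. The protocol does not support that. Objective 3 is asked by severity level and therapeutic group, and the severity mix does not move results within a level. Outcomes unrelated to severity do not move either.
- **Half the sites need not mean half the patients.** Sites restricted to severe disease may recruit fewer. The shift at w = 0.1 is one fifth of that at w = 0.5. This stands, and it is why only a range can be given.
- **The 2010 sampling is barely described.** A reader might infer that the earlier sample was certainly unenriched. Table 1 shows no severe-only arm but does not describe how patients were sampled, and section 5.2 says the two studies are methodologically tied. A false difference from 2010 is therefore conditional.

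Over-sampling severe patients is itself defensible, given the interest in high need and in systemic treatment.

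**Conclusion.** The point holds for pooled, unweighted estimates of severity-dependent outcomes, that is, Objectives 1, 4, 5, 7, 9 and 10 to the extent that their outcomes vary with severity. The direction is certain whenever the severe-only sites contribute patients and the all-severity sites are not wholly severe. The size is not: it runs from 0.06D to 0.45D over the assumed ranges of w and s.

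For the 13.3% benchmark, an assumed 10-point gap and s = 20% give a false difference in about 88%, 36% or 10% of studies at w = 0.5, 0.25 or 0.1, provided that the 2010 sample was not similarly enriched. The protocol does not establish any single one of these figures. What it does establish is that the enrichment and the claim of representative data comparable with 2010 stand side by side without being reconciled.

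**What to change.** 1. Record the site type (all severities or severe only) for each patient.
2. State in section 6.9 that whole-population estimates and the 2010 comparison use the all-severity sites only, or all patients weighted to the severity distribution at those sites. If weighting is chosen, state the assumption that severe patients are alike at both types of site.
3. Use the severe-only sites for estimates within severe disease, where the enrichment is useful.
4. Add the severity condition for those sites to section 6.3.2, with one recruitment definition that all of them apply, and mention the split in 6.1 and the synopsis.
5. In section 5.2, limit the word representative to the all-severity or weighted analysis. Even there it needs a caveat, because section 6.4 has sites only partly selected at random, with an expected participation rate of 15%.

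The cost is protocol wording, one data field, possibly a weight, and some precision. Under equal recruitment the 95% half-width for a 50% proportion is about 3.6 instead of 2.5 points with the all-severity sites alone (n about 750). With weighting, the effective n is about 825 to 1,050. Both are before clustering by site.

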6.3.2 Inclusion criteria

Inclusion criteria are:

- Age 18 or older
- Diagnosed atopic dermatitis
- Patient understands the survey and is expected to be able to complete the questionnaire
- Patient gives written consent on participation
- Patient has signed the data protection declaration

6.3.3 Exclusion criteria

Exclusion criteria are:

• lack of mental, physical or linguistic ability to participate in a questionnaire survey

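### Eligibility neither excludes nor identifies patients whose atopic dermatitis treatment is assigned in an interventional trial, so routine-care estimates of systemic supply and direct costs could include trial treatment

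*Protocol*

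**What the plan says.** The synopsis gives the objective as "Generating routine data on quality of care, treatments needs, and guideline- compliant care for atopic dermatitis" and the design as "Non-interventional, multi-center, cross-sectional health care study in patients with atopic dermatitis under medical care". Section 5.2 adds that the results are to serve the "scientific analysis of the current supply of care with topical therapy and systemic drugs" and to support argument towards payers and decision-makers.

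Section 6.3.2 has one clinical inclusion criterion, "Diagnosed atopic dermatitis". The others are age 18 or older, ability to complete the questionnaire, consent and a signed data protection declaration. Section 6.3.3 has a single exclusion, "lack of mental, physical or linguistic ability to participate in a questionnaire survey". The synopsis adds no further restriction.

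Section 6.3.1 plans about 100 active sites, of which roughly 50 take all severity levels. Of the others it says: "The remaining sites should only include patients with severe atopic dermatitis". Section 6.2 asks about undersupply, with emphasis on systemic drugs (objective 7), and "How high are the costs-of-illness caused by atopic dermatitis and which predictors can be found" (objective 9).

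**The concern.** Therapy that a trial protocol assigns does not show what routine care supplies, and drug that a trial sponsor provides is not a routine cost. Nothing in the written criteria keeps a trial participant out of the sample or makes one recognisable in the data. The word non-interventional describes this study, not the patient's other treatment, and being under medical care does not rule out being in a trial.

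Three results are exposed:

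- **Systemic supply (objective 7).** A trial patient on an active systemic would count as supplied although routine care did not supply the drug. A patient on blinded treatment could not be classified.
- **Direct costs (objective 9).** Section 6.8 has a health economist turn entries into costs but gives no rule for drug supplied free by a trial. Pricing it at zero and pricing it as a routine prescription give different answers.
- **PBI by therapy, secondarily.** Benefit reported for systemics could mix investigational with routine treatment.

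The first two matter most among severe patients, to whom about half the sites are dedicated. A larger sample does not remove such a bias, so the power statement in section 6.7 offers no protection. A statistical analysis plan could not repair it later unless participation had been recorded.

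**Working it through.** The protocol has no figure of its own to reproduce on this point. The check has two parts.

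**1. Eligibility.** Take an adult with diagnosed atopic dermatitis who is in a drug trial, can complete a questionnaire and signs both forms. Every criterion in 6.3.2 is met and the exclusion in 6.3.3 does not apply, so the patient is eligible. This follows from the text and needs no assumption.

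**2. Possible size, for systemic use among severe patients.**

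Inputs:
- Number of severe patients, n = 750. This is an assumption: 50 severe-only sites (6.3.1) at 15 patients each, where 15 = 1,500/100. Severe patients from the all-severity sites would add to it.
- Routine systemic use, p = 30% (assumption; the protocol gives none).
- Share of severe patients in a treatment-assigning trial, f = 3% to 10% (assumption; the protocol gives none).
- Proportion of trial patients recorded as on a systemic, q = 100% (the extreme case).

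Formulas: observed use = (1 - f) × p + f × q, so the shift is f × (q - p).

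- f = 3%: 750 × 0.03 = 22.5 patients. Observed use = 0.97 × 30% + 3% = 32.1%, a shift of +2.1 points.
- f = 10%: 750 × 0.10 = 75 patients. Observed use = 0.90 × 30% + 10% = 37.0%, a shift of +7.0 points.

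Sampling error for comparison: 1.96 × sqrt(0.30 × 0.70 / 750) = 3.3 points. The shift exceeds this once 0.70 × f > 3.3 points, that is, above a trial share of about 4.7%.

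Sensitivity to q: if only half the trial patients are recorded as on a systemic (q = 50%), the shift is f × 20 points, or +0.6 to +2.0 points. Both values lie within sampling error. If q falls below p, for example because most are in topical trials, the shift changes sign.

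**Cost of setting flagged patients aside.** At f = 10% the denominator falls from 750 to 675, and the half-width becomes 1.96 × sqrt(0.21 / 675) = 3.5 points. If 1,500 unflagged patients were wanted overall and 10% of all patients were flagged, 1,500 / 0.90 = 1,667 would be needed. That is inside the 1,500 to 2,000 range of section 6.3.1.

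**The case against.** The strongest case on the other side is that the protocol is silent rather than wrong. It does not say that trial participants will be enrolled, how many there are, or that the sites run trials. Section 6.4 describes practices and ambulant clinics, partly chosen at random. The questionnaires are not shown and might already ask the question, and section 6.5 (step 2e) leaves the forms to be finalised. Section 6.8 has a physician categorise treatment entries and an economist check cost data, and a trial drug might be noticed at either step. All of this stands, and it limits the point to what could happen. A reader might infer that trial therapy, tests and free drug are in fact being counted as routine care. The documents do not support that.

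Two further inferences also fail:

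- **That undersupply is understated by 2-7 points.** The arithmetic moves systemic use. Undersupply also needs a definition of need, which section 6.5 (step 2b) leaves to be refined.
- **That the process indicators are inflated by trial procedures.** Most of the 12 indicators in section 6.6.1, such as smoking at home, education classes, house-dust measures and history of atopy, are not obviously set by a trial protocol.

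There is also a fair objection to excluding such patients. The study is tied to AtopicHealth1 (5.2), and objective 4 compares with 2010. Nothing in the protocol says that AtopicHealth1 excluded trial participants. A new exclusion could disturb that comparison, and it could also remove patients whom routine care had failed.

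None of this closes the gap. The steps in section 6.8 do not mention trial participation, and a drug name alone may not reveal it.

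**Conclusion.** The point holds as a gap in eligibility and data capture. Patients whose atopic dermatitis treatment is assigned in an interventional trial can enter and are not identified, which fits poorly with the routine-care aim. The results chiefly exposed are systemic-drug supply and direct costs, with PBI by therapy second.

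The size is unknown. The 2-7 point shift in systemic use is an illustration. It rests on an assumed 3-10% trial share, 30% routine use, 750 severe patients, and every trial patient being recorded as on a systemic. Its lower end lies within the 3.3-point half-width, and the shift shrinks if some patients are on placebo or in topical trials. No figure can be put on costs, because the direction depends on a pricing rule that the protocol does not state. This is a minor improvement, worth making because it is cheap and cannot be made after data collection.

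**What to change.** Add one yes/no item to the physician form, while the forms are still being finalised (6.5, step 2e): is the patient currently taking part in an interventional trial that assigns treatment for atopic dermatitis? State that participation in a registry such as TREATgermany does not count.

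Report systemic supply, PBI by therapy and costs without flagged patients. Give the all-patient result as a sensitivity analysis, which also serves the comparison with AtopicHealth1. No new exclusion criterion is needed.

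The cost is one extra form item and a slightly smaller denominator for these results. No patient is lost from the study, and the planned sample size range need not change.
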